To date, four pilot studies have evaluated interventions exclusively designed for parents of young children with T1D, but only two have shown any impact on improving children's glycemic control.³¹⁻³⁴ Specifically, in one study, a multifamily in clinic group education program was trialed and the results demonstrated lower HbA1c levels among children for the 41% of parents who attended >3 groups versus the 59% of parents who attended fewer groups.³¹ However, the study was not randomized, the intervention was delivered during children's T1D clinic appointments, and the non-attenders also had a significantly lower attendance rate at their child's routine T1D clinic appointments making it difficult to solely ascribe changes in children's HbA1c levels to the intervention. The second study is part of our own preliminary work. In this study, we also piloted a multifamily group treatment program for parents. Nine families participated (M child age 5.0±1.2 years; see Preliminary Studies).³³ Our BEST MEALS intervention showed a 26 mg/dl decrease in children's average daily glucose levels (185±46 v 159±40 mg/dl, pre- to post-treatment, respectively, p<0.001) with virtually no change in children's rate of hypoglycemia, suggesting the intervention helped parents to safely improve their child's daily glycemic levels. We also found an improvement in mealtimes and parents reported a high level of treatment satisfaction. However, our pilot study was also not randomized, the treatment was parent-based and delivered face-to-face (limiting its scalability) and the content was highly focused on mealtimes. The treatment outcome literature for young children with T1D is limited, but preliminary studies and our own pilot work suggests: (1) families are interested in participating in behavioral interventions, (2) interventions focused on age-appropriate T1D education and reducing disruptive child behavior can lead to improved child glycemic levels. Additional work is needed to build on these preliminary studies to increase the generalizability and impact of these behavioral interventions.

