One way to consider increasing the impact of existing interventions for families of young children is to modify their mode of treatment delivery from face-to-face encounters and in clinic visits to a more modern technology-based method using the internet or a cellular phone. Behavioral interventions are typically labor and time-intensive, which can limit their impact and feasibility.^{35, 36} But using technology to deliver a behavioral intervention, while not a short-cut to intervention, could enhance both its generalizability and scalability by minimizing traditional barriers to participation, including travel to the medical center, child care, and time off from work.³⁵ Also, for families of children with T1D, a technology-based intervention may be more feasible than an in clinic intervention because at most, youths are seen only quarterly and data suggest that the majority of families attend fewer than four diabetes clinic appointments per year.³⁷ There is growing evidence showing acceptability of internet interventions in adolescents with T1D³⁸⁻⁴¹ and their parents.⁴² In three of these studies,³⁹⁻⁴¹ the interventions resulted in improved T1D self-care. Two studies showed improvements in self-efficacy and quality of life,^{38, 42} while one study showed an effect for youths' HbA1c.⁴¹ Specific to mobile technology ("mHealth"), several studies have investigated the impact of using text messaging in adolescents and adults with T1D⁴³⁻⁴⁶ and one study compared text messages versus email.⁴³ In this study, both email and text message recipients experienced a short-term improvement in adherence, but the researchers noted a drop off in the use of these technologies after 3 months. It is possible that this drop off occurred because of the type of messages youths received which were only generic reminders to complete self-monitoring glucose checks versus more personalized feedback and reinforcement.⁴³ However, the emergence of more advanced communication technology now makes it very feasible to offer patients' personalized feedback to enhance intervention.⁴⁴ In short, using technology is a smart way to address the barriers to traditional face-to-face intervention that families articulate. Internet and mHealth interventions are feasible and acceptable in families of adolescents with T1D. Also, as packaged interventions for delivery via the internet or by cellular phone, these interventions would be easy to disseminate across centers.

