Human Subjects Involvement, Characteristics, and Design

Aim 3 will involve a randomized pilot test (RPT) of DIPPer Academy. We propose to enroll up to 50 parents of young children with T1D into the RPT. Parents who participate will be randomized to either an immediate treatment or a control group. Parent will be recruited via letter, telephone call, or in clinic. Parents will be asked to give written informed consent for their participation and permission to obtain a measure of HbA1c level in their child. Parents will be asked to complete study assessments (online surveys) at Time 1 (baseline), Time 2 (post-treatment), and Time 3 (follow up). We will collect child HbA1c at Times 1, 2, and 3. We anticipate that parents may spend about 3 hours completing the DIPPer Academy curricula spread out across 14 weeks of treatment. We expect the surveys at Times 1, 2, and 3 will each time take about 20 minutes to complete.

All parents regardless of gender, race, ethnicity, and socioeconomic class will be considered potentially eligible to participate. Specific inclusion criteria for parents are:

1. Parents of a young child who is between 3-5 years old and at least 3 months post T1D diagnosis.
2. Parents who are English-speaking.

Parent exclusion criteria for are:

1. Young children with evidence of type 2 diabetes or monogenic diabetes.
2. Parents with evidence of severe psychiatric disorder.
3. Young children with a comorbid chronic illness (e.g., renal disease) that requires ongoing care beyond T1D.
4. Young children with a history of anemia or medication use that may interact with glycemic control (e.g., systemic steroids).
5. Young children with an HbA1c $\leq 7.5\%$ (which is the current ADA target).⁶

Sources of Materials

For all participating parents, we will collect demographic data and medical history data specific to T1D. We will also collect data via parent surveys and usage data collected during the intervention (i.e., website use statistics). Survey and parent usage data will be entered and stored in an electronic database (REDCap). This database will be located on a secured server maintained by the Department of Biostatistics at KUMC. No one outside of the research team will have access to data identifying the families who participated. We will obtain a measure of child HbA1c.

Potential Risks

The overall risks of participation in this project are no more than minimal.

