3. We propose to collect children's HbA1c levels at Times 1, 2, and 3 during the randomized pilot trial. The purpose of measuring children's HbA1c levels will be to explore the impact of DIPPer Academy on children's glycemic control even though children will not participate in the intervention.
4. Participating may inconvenience parents. We will minimize the potential risk of inconvenience by offering parents the opportunity to participate in a project from their home. If parents do not own a mobile device or would prefer not to use their personal mobile device to access DIPPer Academy, we will loan parents an iPad Mini with data plan for use during the study. Prior to informed consent, parents will be informed

of their ability to discontinue participation in a research project at any time without penalty. Discontinuation from a research project will not impact a child's care by their Diabetes Team. The PI will ensure that research staff is trained to explicitly inform parents of the purpose, procedures, and risk related to participating in one of these research projects.

5. We hypothesize that DIPPer Academy will be deemed feasible and acceptable by parents and will have a beneficial effect on children's HbA1c. We have attempted to minimize the potential risk of inconvenience to parents participating in DIPPer Academy by designing the intervention as a mHealth intervention. Parents will be able to access the DIPPer Academy website from their computer or any mobile device. From the website, they will be able to view the video microlectures at any time and as often as they wish.
6. [name] will be available to provide medical supervision.

POTENTIAL BENEFITS OF THE PROPOSED RESEARCH TO THE SUBJECTS AND OTHERS

There is a chance parentss will perceive no direct benefit to study participation. In this case, parents who elect to participate have the opportunity to contribute to our evolving knowledge related to glycemic control in children with T1D and the development of preventative interventions to promote optimal glycemic control in young children with T1D.

IMPORTANCE OF THE KNOWLEDGE TO BE GAINED

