Hypothesis 4: DIPPer Academy will result in greater reported Time 2 parent self-efficacy and lower reported post-treatment parenting stress, mealtime behavior problems and hypoglycemia fear than standard of care, controlling for Time 1 measurements on these variables.

Data Analyses. For the primary outcomes, we will conduct a sensitivity analysis to test for any effects due to attrition. We will also use an intent-to-treat strategy and imputation model to examine parent data even if they are lost to attrition. For all analyses, we will include parental depression as a covariate if determined to be correlated with our outcome variables. To test for between group differences in glycemic levels (Hypothesis 1), we will conduct an ANCOVA with Time 2 (post-treatment) score as the outcome, group (treatment vs. control) as focal predictor, and Time 1 (baseline) score as covariate. In addition, we will calculate within group standardized effect sizes (in SD units) and within-group changes for HbA1c based on Time 1 and Time 2 values. To estimate and test time trends in glycemic levels for DIPPer participants (Hypothesis 2) we will use appropriate generalized mixed models with a random parent intercept to account for clustering of repeated measures within parents. Finally, to test for post-treatment differences between groups in reported parent self-efficacy, parenting stress, mealtime behavior problems, and hypoglycemia fear (Hypothesis 3) we will calculate within group standardized effect sizes (in SD units) and within group changes for parents' PSESDM, PIP, BPFAS, and HFS-PYC scores using parents' Time 1 and Time 2 data. To test for statistical significance, we will conduct an ANOVA for each variable as described above for Hypothesis 1.

REFERENCES

1. Liese, A.D., et al., *The burden of diabetes mellitus among US youth: prevalence estimates from the SEARCH for Diabetes in Youth Study*. Pediatrics, 2006. **118**(4): p. 1510-8.
2. Vehik, K., et al., *Increasing incidence of type 1 diabetes in 0- to 17-year-old Colorado youth*. Diabetes Care, 2007. **30**(3): p. 503-9.
3. Dabelea, D., *The accelerating epidemic of childhood diabetes*. Lancet, 2009. **373**(9680): p. 1999-2000.
4. Patterson, C.C., et al., *Incidence trends for childhood type 1 diabetes in Europe during 1989-2003 and predicted new cases 2005-20: a multicentre prospective registration study*. Lancet, 2009. **373**(9680): p. 2027-33.

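### Does the SAP need a usage or retention analysis because the protocol hypothesises that parents will find DIPPer Academy feasible?

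*Combined protocol and SAP*

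**What the plan says.** Item 5 of the list under Minimization of Risks states "We hypothesize that DIPPer Academy will be deemed feasible and acceptable by parents", and the same sentence goes on to expect a benefit on children's HbA1c. Viewing is self-paced: from the website "they will be able to view the video microlectures at any time and as often as they wish". The design section gives the expected exposure: "We anticipate that parents may spend about 3 hours completing the DIPPer Academy curricula spread out across 14 weeks of treatment". Sources of Materials lists "usage data collected during the intervention (i.e., website use statistics") among the data collected and says that they are stored in REDCap.

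The Data Analyses paragraph of the SAP contains:

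- an attrition check: "For the primary outcomes, we will conduct a sensitivity analysis to test for any effects due to attrition";
- intent-to-treat with an imputation model;
- parental depression as a possible covariate;
- an ANCOVA of Time 2 HbA1c on group and baseline;
- mixed models for the HbA1c trend in DIPPer participants;
- effect sizes and tests for four parent-reported scales.

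The Data and Safety Monitoring Plan describes a summary covering recruitment, retention and protocol adherence, to be prepared for DSMB meetings if the IRB asks for a DSMB. In the hypothesis list nothing follows the label for Hypothesis 3.

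**The concern.** In a randomised pilot of a self-paced programme, whether parents use it is one of the main things to learn. The plan names feasibility as an expectation and collects data that bear on it, but the visible analysis text does not use those data. The attrition provisions do not fill the gap, because non-use differs from loss to follow-up: a parent can complete every Time 2 survey without opening a video.

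The background gives reason to expect uneven engagement. A cited group programme found "lower HbA1c levels among children for the 41% of parents who attended >3 groups versus the 59% of parents who attended fewer groups", and in a cited messaging study "the researchers noted a drop off in the use of these technologies after 3 months". DIPPer Academy runs for 14 weeks.

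Two things could be at stake. A null HbA1c comparison could mean an ineffective programme or an unused one. And if the terms completed and feasible are defined only once usage has been seen, a claim of feasibility carries little weight.

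**Working it through.** **1. Text check.** The plan states no figure for feasibility, completion or power, so there is nothing of its own to reproduce. Setting the sections side by side:

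| Item | Where it appears | Analysis in the visible SAP |
|---|---|---|
| HbA1c benefit | Risk section; Hypotheses 1 and 2 | ANCOVA; mixed model |
| Parent scales | Hypothesis 4 (labelled Hypothesis 3 in Data Analyses) | Effect sizes and a test for each scale |
| Feasible and acceptable to parents | Risk section only | None visible |
| Website use | Sources of Materials | None visible |
| Retention | Conditional DSMB summary | Only as attrition in the primary outcomes |

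So the observation is accurate for the visible text. The numbering mismatch leaves two readings of the empty Hypothesis 3: a numbering slip, or text missing from the public copy that may have concerned feasibility. The documents do not settle which.

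**2. What non-use would do to the HbA1c comparison.** From the documents: up to 50 parents, and 41% attending more than 3 groups in the cited programme. Assumed: 25 per arm, no loss, two-sided 5% level, and a correlation r between Time 1 and Time 2 HbA1c of 0.6 (range 0.4 to 0.8).

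The standard error of the adjusted difference, in SD units, is √(1 − r²) × √(2/25). At r = 0.6 this is 0.8 × 0.283 = 0.226. With 47 degrees of freedom (50 − 3) and the noncentral t distribution, the difference detectable with 80% power is:

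- r = 0.4: 0.74 SD
- r = 0.6: 0.65 SD (0.647)
- r = 0.8: 0.49 SD

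If a fraction u of parents use the programme and the others gain nothing, the group difference is u times the effect in users. For an effect of 0.647 SD in users at r = 0.6:

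| Use u | Group difference (SD) | Power |
|---|---|---|
| 100% | 0.647 | 80% |
| 80% | 0.518 | 61% |
| 41% | 0.265 | 21% |

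To keep 80% power at 41% use, the effect in users would have to be 0.647/0.41 = 1.58 SD (1.81 at r = 0.4, 1.18 at r = 0.8).

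**3. How far those figures carry.** The cited 59% attended fewer groups; the protocol does not say that they attended none. If, for illustration, they gained half the effect, the group difference would be 0.41 + 0.59 × 0.5 = 0.705 of the full effect. Power would then be 51%, and the required effect 0.647/0.705 = 0.92 SD. The answer therefore depends on an assumption that the documents do not supply, and 41% describes attendance at clinic groups, not viewing of online videos.

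The messaging study adds little. Fourteen weeks is 98 days and three months about 91 days, so a fall in use after three months would touch only about the last week. The protocol also suggests that the generic content of those messages may explain the fall.

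**4. What a written usage analysis would change.** The HbA1c ANCOVA, its power and its validity are the same with or without a usage table. A pass mark would be fragile at this size. Suppose feasibility required the lower Wilson 95% limit for completion to exceed 41%. With 25 parents, 15 completers give 40.7% to 76.6% (fail) and 16 give 44.5% to 79.8% (pass). The binomial probability of at least 16 completers is 42% when true completion is 60%, and 81% when it is 70%. Such a rule would reject a programme with 60% completion 58% of the time, and its threshold would be borrowed from another kind of intervention.

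**The case for a change.** The strongest argument for a change is that the trial is a pilot, that its results are meant to inform a further technology-based intervention, and that one SAP paragraph fixed before anyone sees usage would protect any feasibility claim from hindsight. The conditional DSMB summary is no substitute: it may never be produced, and it sets no criterion.

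Part of this stands. The visible text does not describe a usage summary, and a completion cut-off chosen after looking at the logs would have to be reported as post hoc. That is a matter of honest labelling in the report.

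The rest does not carry. The quoted sentence is about what parents deem feasible and acceptable. The direct evidence for that is a parent rating, as in the team's earlier pilot, where "parents reported a high level of treatment satisfaction". Whether such a rating is collected here cannot be told from the public text. Viewing counts would answer a different question, under a definition of feasibility that the plan does not use. The sentence also sits in a risk section, where it introduces how inconvenience is limited, and is not in the visible list of hypotheses to be tested. With no feasibility threshold or decision rule in the plan, no stated rule can give a wrong answer.

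**Conclusion.** This is a gap in description that analysts fill sensibly, and the plan can stand. Website use is stored, and follow-up status is needed for the planned attrition analysis. Reporting use among all parents randomised to DIPPer Academy, and retention at Times 2 and 3 by arm, is ordinary descriptive work that needs no advance rule. The HbA1c and parent-scale analyses are not affected.

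Non-use could matter a good deal for interpreting a null result: power of 21% to 51% at the cited 41% engagement, depending on whether less engaged parents gain nothing or half the effect. Those figures rest on assumed arm sizes, no loss and a correlation of 0.6, and they describe a limitation of a small pilot that a usage paragraph would not remove. The conclusion is confined to the public text. The empty Hypothesis 3 and the absence of a visible measures section mean that the full plan may already address feasibility or acceptability.

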Before the proposed projects begin, we will obtain approval from the Institutional Review Board (IRB) at Children's Mercy Hospital (CMH). The PI will also secure approval from her home institution, the University of Kansas Medical Center, to Rely on the IRB at CMH as the IRB of record for the projects. In compliance with regulatory practices, the PI and Co-Investigators will secure "continuing approval" for the research projects each year from the CMH IRB and will notify the CMH and KUMC IRB's if any Adverse Events (AEs), Other Reportable Information and Occurrences (ORIOs), and Unanticipated Problems Involving Risks to Subjects or Others (UaPs) occur in the conduct of the projects. The PI (with the assistance of Co-Investigators, as needed) will assume primary responsibility for reporting AEs, ORIOs, UaPs, or unforeseen outcomes to the IRBs in a timely fashion and will promptly inform the study sponsor of any action taken by the IRB at CMH because of continuing review. The proposed research designs have been developed keeping in mind how to maximize specific data collection and minimize risk to parents (i.e., psychometrically sound and benign questionnaires, [name] availability to provide medical supervision of patients). However, at the discretion of the CMH IRB, the PI will recruit a Data Safety and Monitoring Board (DSMB) to oversee and monitor the data collection and intervention delivery. We propose members of the DSMB will include an endocrinologist, a psychologist, and a certified diabetes educator. If a DSMB is requested by the CMH IRB, we propose that the DSMB will meet at least annually by teleconference. For each of these meetings, the PI and the biostatistician will jointly prepare a summary of the following topics:

Performance monitoring: A report of subject recruitment/retention, protocol adherence, and quality of data collection procedures.

Safety monitoring: A review of safety of the participants, including confidentiality and any adverse events or side effects related to the study procedures.

STATISTICAL ANALYSIS PLAN

Hypotheses:

Hypothesis 1: DIPPer Academy will result in better Time 2 HbA1c than standard of care controlling for Time 1 measurements.

Hypothesis 2: DIPPer Academy will result in improvements in HbA1c across time (a decreasing time trend for HbA1c).

Hypothesis 3:

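### The only described safety summary is worded around events related to study procedures, with no adverse-event table by arm, so it could not reliably show or exclude an excess under DIPPer

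*Combined protocol and SAP*

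**What the plan says.** The Data and Safety Monitoring Plan has three relevant elements.

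- **Individual notification.** The investigators "will notify the CMH and KUMC IRB's if any Adverse Events (AEs), Other Reportable Information and Occurrences (ORIOs), and Unanticipated Problems" occur. No relationship or arm restriction is attached. The CMH IRB also renews approval every year, but what that review receives is not described.
- **A conditional summary.** "If a DSMB is requested by the CMH IRB, we propose that the DSMB will meet at least annually by teleconference". The PI and the biostatistician prepare a summary for each such meeting.
- **The safety content of that summary.** "A review of safety of the participants, including confidentiality and any adverse events or side effects related to the study procedures". The words at issue are "any adverse events or side effects related to the study procedures".

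On design, the section on Human Subjects Involvement, Characteristics, and Design states: "Parents who participate will be randomized to either an immediate treatment or a control group". Surveys and child HbA1c at Times 1, 2 and 3 are described for participants generally, not for one arm. The Statistical Analysis Plan compares HbA1c and the parent-reported scales between arms and does not mention adverse events. The documents give no adverse-event definition, no method or schedule for asking about events, and no procedure for judging relationship.

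**The concern.** Randomisation allows causation to be judged by comparing all events between arms, without anyone ruling on single cases. If events must first be judged related to study procedures, the comparison depends on those judgements, and no attribution procedure or blinding to arm is described.

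This matters most for events that resemble the underlying disease. The programme aims to lower HbA1c, and the opening background notes that young children with type 1 diabetes already experience hypoglycemia. Under Minimization of Risks, item 3, the children are said not to take part in the intervention; their only described study procedure is the HbA1c measurement. A low glucose at home would therefore be hard to call related to a study procedure in either arm. The investigators' earlier uncontrolled pilot supported its safety conclusion with the overall hypoglycemia rate. This trial plans no hypoglycemia-rate outcome, only a hypoglycemia-fear scale, so an adverse-event summary is the natural place for such a signal to appear.

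**Working it through.** The documents give no event rate, attribution rule or safety threshold, so there is no plan figure to reproduce. The check is a reading of the text followed by an illustration with assumed figures.

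**1. Scope, side by side.** Notification to the IRBs covers any adverse event. The DSMB summary covers participant safety, with "any adverse events or side effects related to the study procedures" as a named component. The two scopes differ within one section. Individual notices are not a tally by arm, and no such tally is specified elsewhere.

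**2. What an attribution filter does.** Let p_T and p_C be the true proportions of families with an event (DIPPer, control), and s_T and s_C the shares judged related. The reviewed proportions are p_T × s_T and p_C × s_C. The reviewed ratio is therefore the true ratio multiplied by s_T / s_C, and the reviewed difference is p_T × s_T − p_C × s_C. All values below are assumed.

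| True DIPPer v control | s_T, s_C | Reviewed | True difference | Reviewed difference |
|---|---|---|---|---|
| 24% v 8% | 1/6, 0 | 4% v 0% | 16 points | 4 points |
| 30% v 10% | 0.2, 0 | 6% v 0% | 20 points | 6 points |
| 30% v 10% | 0.5, 0.5 | 15% v 5% | 20 points | 10 points |
| 30% v 10% | 0.5, 0.1 | 15% v 1% | 20 points | 14 points |
| 20% v 20% | 0.5, 0.1 | 10% v 2% | 0 points | 8 points |

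The first row is 6/25 v 2/25 reviewed as 1/25 v 0/25, assuming 1:1 allocation of 50; the plan states no ratio. Where almost nothing is judged related in either arm, as is plausible for hypoglycemia at home, both reviewed figures approach zero whatever the true rates. The last row shows the opposite error, an apparent excess where there is none. An even filter preserves the ratio but halves the difference in the third row. In the fourth row an uneven filter turns a ratio of 3 into 15. Without knowing s_T and s_C, the reader cannot recover p_T and p_C.

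**3. What a complete table could show.** With 25 per arm and two-sided alpha 0.05 (both assumed), exact Fisher power is about 20% for 5% v 20%, 30% for 10% v 30%, and 59% for 10% v 40%. Even 6/25 v 2/25 gives a Fisher p of about 0.25. No events in 25 gives a one-sided 95% upper limit of 1 − 0.05^(1/25) = 11.3%. The complete table would be descriptive, not a powered comparison.

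**The case against.** The sentence says the review of safety is to include these items, so the list is not closed, and the qualifier about study procedures may attach to side effects alone. Any adverse event goes to both IRBs, and yearly continuing review exists. All of this stands. A reader might infer that safety review is confined to related events, or that the DSMB summary is the only aggregate review. The documents do not support either: the wording is ambiguous, and the content of continuing review is simply not described.

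A reader might also infer that most control-arm events would be left out. No event rates or attribution rules are given, and control families undergo study procedures too, so the documents do not establish this. Nor do they say who judges relationship, only who prepares the summary. Nor does the filter make an excess impossible to show: if control events are screened out more heavily, a DIPPer excess is inflated.

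Finally, this is a small pilot of video lectures for parents, described as carrying at most minimal risk. That limits how much the point weighs. It does not remove it, because on any parsing of the sentence nothing requires all events to be set out by arm.

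**Conclusion.** The concern holds in a limited form. The one safety summary whose content is described is conditional on an IRB request and is worded around relationship to study procedures. No by-arm tabulation of adverse events is planned. As worded, it could not reliably show or exclude an excess of expected-looking events in the DIPPer arm. The claim that it could never show one goes too far.

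The size of any distortion is unknown. In the illustration a true 16-point difference shrinks to 4 points, and a true difference of zero becomes 8 points. These figures rest on assumed event rates and attribution shares, and the first also on 25 families per arm. With "We propose to enroll up to 50 parents of young children with T1D into the RPT" as the ceiling, even complete counts would be descriptive. The importance is minor to moderate: worth correcting because it is cheap and because events not asked about may not be recoverable later.

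**What to change.** Reword the safety item in the Data and Safety Monitoring Plan to: *all adverse events in participating parents and their children, asked about in the same way in both arms at Times 1, 2 and 3, tabulated by randomised arm regardless of judged relationship, with relationship as a separate column.* Time 1 answers serve as the baseline; the comparison rests on the later assessments. Asking in the same way in both arms is essential, because a table built only from spontaneous reports could reflect unequal ascertainment.

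Prepare the same table for the yearly CMH IRB continuing review if no DSMB is convened, and report it with the trial results.

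The cost is one reworded sentence, a short added question at assessments already planned, and one table. The table will contain more background events, and its counts should be presented descriptively, without a claim to have tested safety.
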